#### **E. Chart Review**

1. List the data that will be used from the chart review. Alternatively, attach a separate data collection tool.

The chart review is prospective in nature. We will collect individuals' basic characteristic and clinical variables, including date of birth, race/ethnicity, gender, insurance type, residential zip code, smoking history, height, weight, history of COVID vaccination, previous history of COVID, dexamethasone adverse events such as hyperglycemia, infections etc, respiratory support including nasal cannula oxygen, high flow oxygen, Bipap, mechanic ventilation, length of ICU stay, length of hospital stay, discharge disposition, health status 28 days after first dose of study dexamethasone eg. supplemental oxygen, tracheostomy, chronic mechanic support, daily activity limitation. We will also examine comorbidities including obesity, diabetes,

hypertension, hyperlipidemia, acute kidney injury, chronic kidney disease, heart failure, arrhythmia, coronary artery disease, psychological disease etc.

2. Describe the databases that will be utilized, including specific sites from which you will collect data.

We will collect data from Meditech database in OUMC.

3. Describe the process for obtaining and recording the records and at what point (if at all) the data is de-identified.

The investigators conduct a review of records from their practice and collects medical records based on inclusion/exclusion criteria. Records will be de-identified during data analysis.

4. Explain how access to the data will be controlled and whether the access is logged.

The electronic images of signed consent forms will be stored in a secured server in OUHSC campus. This secured server will be created with OUHSC IT service help. Only study team members have the access to the secured server. The data abstracted from Meditech will be stored in REDCap. Only research team members have the access to REDCap.

5. What happens to the data at the end of the study?

The electronic data will be stored in the secured server and REDCap after the project closure for future research reference.

**F. Biospecimens**

No biospecimens will be collected.

**G. Banking/Repository/Database**

Our Pulmonary Section of Department of Medicine plan to have long term research on respiratory failure due to COVID, including retrospective and prospective research. The data in this study will be important reference for future research. The electronic data will be stored in the same secured server in OUHSC. Only the study team members have the access to the data. PI will log into the server once per month to ensure the database function after the study is closed. PI will report to OUHSC IT for any concern regarding the database security. The data in REDCap will follow the regulation of OUHSC REDCap policy.

**H. Inclusion / Exclusion Criteria**

1. List the criteria that will define who will be **included** in the study

Age  $\geq$  18 years old

PCR confirmed COVID-19 infection

Positive pressure ventilation (non-invasive or invasive) or high flow nasal cannula (HFNC) or need supplemental oxygen with oxygen mask or nasal cannula

2. List the criteria that will define who will be **excluded** in the study.

Underlying disease requiring chronic corticosteroids

Severe adverse events before admission, i.e. cardiac arrest;

Contraindication for corticosteroids;

Death is deemed to be imminent and inevitable during the next 24 hours

Recruited in other clinical intervention trial

Pregnancy

Patient on judicial protection

3. Provide early termination criteria.

The study will be terminated early if COVID pandemic ends or there is no new COVID admission to OUMC or the interim data analysis (6 weeks after study start date) shows worse primary outcome in intervention group.

**I. Gender/Minority/Pediatric Inclusion for Research**

Male and female adults will be included in the study. This study will be conducted in OUMC adult service. We will exclude participants age < 18 years old.

**J. Recruitment and Enrollment**

1. Describe the plans for recruitment.

a. Methods to identify and recruit potential participants

The participants will be identified when the ICU service or the hospitalist service providers are contacted for admission. The providers will review all the clinical data and decide if the potential participants meet the inclusion criteria and contact the investigators.

b. If this is a multicenter study where subjects will be recruited by methods not under control of the local site (call centers, national advertisements), indicate this here.

This is not a multicenter study.

2. Describe the consent procedures to be followed

If the potential participant is able to consent him/herself (or at least assent), the potential participant will read and sign the consent form himself/herself. The paper consent form does not leave the patient room. Instead, the signature page is pressed up against the glass and the investigator takes a picture of the signature pages with his/her cell phone.

If the potential participant is not able to consent/assent and consent is obtained from the power of attorney who is not physically present, consent is

IRB NUMBER: 12927  
IRB APPROVAL DATE: 01/15/2021

obtained over the phone by the investigator with a witness listening. Informed Consent can be obtained verbally over the phone with a legally authorized representative and a witness, and the signed consent can be returned by fax, email or mail. The participant can be randomized and put in the study prior to return of the signed consent, however, if the signed consent is not returned, the participant will be removed from the study.

3. Describe the location where consent is most likely to take place.  
The consent will be obtained while an inpatient (ICU, ER, and medial floor)
4. Describe provisions for recruiting non-English speaking participants.  
The information on the informed consent form will be explained to patients or power of attorney and all questions will be answered using the hospital legal interpreter service before the consent form is signed.
5. Describe measures to decrease participant coercion  
The investigator allows the potential participant adequate time to review the consent, the investigator will answer all the questions the potential participant or power of attorney have before the consent form is signed.

#### **K. Risks and Benefits**

The risks for participants who are on dexamethasone 20mg daily group may have higher risk of dexamethasone adverse effects such as infection, hyperglycemia etc.(7) The high dose dexamethasone has been used widely in clinical practice for many years and severe adverse effects are rare. The providers will monitor the adverse effects closely and start appropriate treatment such as antibiotics and insulin. If our study shows dexamethasone 20mg daily therapy group has better health outcome, participants in this group will benefit from this therapy. On the other hand, the participants in dexamethasone 6mg daily group may not have the same good outcome as the dexamethasone 20mg daily group. Using dexamethasone 6mg daily may also cause hyper glycemia and infection etc requiring relevant treatment.

The dexamethasone 20mg\*5 days, then 10mg \*5 days (10 days course) costs \$11.85 (vials) or \$41.43 (tablets). The dexamethasone 6mg daily\*10 days costs \$59.1 (vials) or \$131.9 (tablets). The cost of high dose therapy is lower than the low dose therapy. There should not be extra financial burden to the participants.

Although one clinical trial found dexamethasone 6mg daily for 10 days had mortality benefit compared to usual care without dexamethasone therapy,(4) the difference of health outcome between high dose and low dose therapy is not confirmed. The mental risk to participant is minimal. The investigators will explain the study in details and answer all the questions to release the stress before participants/power of attorney decide to sign the consent.

The information which can be used to identify the participant including name, date of birth will be used only to locate the data in the database. The data will be de-identified during the data analysis process. The data will be stored in a secured server in OUHSC. Only the study team members have the access to the data. Patients' personal information will not be released to public. There may not have direct benefit to the participants if our study does not reveal health outcome difference between the study groups, but the study results will help us to improve the COVID healthcare in general population.

#### **L. Multiple Sites**

This study will be conducted in OUMC only.

We will conduct descriptive statistics to characterize the study population at baseline, the health outcomes and adverse events. Continuous variables will be expressed as mean  $\pm$  SD, while discrete variables will be shown as percentages. A two-tailed p value  $<0.05$  will be considered statistically significant. Between-group comparisons will be made using the independent t-test (for 2 groups) or the ANOVA (for  $>2$  groups). Chi-squared tests will be used to evaluate relationship of two categorical variables. Logistic regression analysis will be performed to determine the association between health outcomes (ordinal scale, length of hospital stay, ICU days, death) and risk factors, adjusted for age and PaO2:FiO2 ratio.

## N. **Data and Safety Monitoring Plan**

Due to the urgent need for effective treatment, an internal data and safety monitoring board will be appointed for monitoring the trial progress. The board includes all project investigators. The board members will meet once per month, usually by teleconference, to review data from this trial. The board is also responsible for review of related issues, such as center performance standards. The board may request more frequent meetings if necessary to fulfill its charge. It may also request additional safety reports on a more frequent basis. The data board will review includes participants' health outcome data such as ventilator support, hospital or ICU length of stay, death, dexamethasone adverse events, such as uncontrolled hyperglycemia requiring insulin infusion, severe infection etc. After each meeting, the board will make formal recommendations regarding trial continuation and clinical performance. A special responsibility of the board is to review serious adverse events (SAEs), as defined by deaths, life threatening conditions, or events requiring permanent discontinuation of the treatment. SAEs are to be documented on case report forms and reported to the primary investigator within 24 hours of notice, with follow up reporting until the event has terminated. The SAEs will also be submitted to OUHSC IRB in a timely fashion for review. According to other clinical trial using the high dose dexamethasone, the risk of insulin use, new diagnosis of infection and SAEs were similar between intervention and placebo. (5) However, if the high dose dexamethasone group has statistically significant worse health outcome compared to the control group, it might trigger an immediate suspension of the study.

At the end of each board meeting, the board will vote whether to continue the study as planned or whether to recommend changes to the study. The board may

recommend that the study be stopped early if there is evidence that the risk-benefit ratio does not warrant continuation of the trial.

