**Abstract**

The coronavirus disease 2019 (COVID-19) pandemic is a serious global health threat. Multiple antiviral or immunomodulatory therapies have failed to show any mortality benefit for patients with COVID-19. Dexamethasone was shown in a large clinical trial to improve mortality. However, it is unclear what dose of dexamethasone is most beneficial in hospitalized patients with COVID-19. We plan to conduct a randomized single center open label clinical trial to evaluate two different doses of dexamethasone (20mg vs. 6mg) on the health outcome for hospitalized patients with COVID-19. The intervention arm is dexamethasone 20mg daily for 5 days, followed by dexamethasone 10mg daily for 5 days. The comparator is dexamethasone 6mg daily for 10 days. Three hundred participants will be enrolled. The primary outcome is clinical improvement using World Health Organization ordinal scale at day 28 or live discharge, whichever comes first. Our hypothesis is that patients who are treated with dexamethasone 20mg daily are more likely to have clinical improvement compare to those who are treated with dexamethasone 6mg daily on day 28.

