### **C. Preliminary Studies/Progress Report**

In RECOVERY trial, 2104 patients were assigned to receive dexamethasone 6mg daily for 10 days and 4321 to receive usual care (no dexamethasone). (4) Overall, 482 patients (22.9%) in the dexamethasone group and 1110 patients (25.7%) in the usual care group died within 28 days after randomization (age-adjusted rate ratio, 0.83; 95% confidence interval [CI], 0.75 to 0.93;  $P<0.001$ ). In the dexamethasone group, the incidence of death was lower than that in the usual care group among patients receiving invasive mechanical ventilation (29.3% vs. 41.4%; rate ratio, 0.64; 95% CI, 0.51 to 0.81) and among those receiving oxygen without invasive mechanical ventilation (23.3% vs. 26.2%; rate ratio, 0.82; 95% CI, 0.72 to 0.94) but not among those who were receiving no respiratory support at randomization (17.8% vs. 14.0%; rate ratio, 1.19; 95% CI, 0.91 to 1.55). This trial concluded that in patients hospitalized with Covid-19, the use of dexamethasone resulted in lower 28-day mortality among those who were receiving either invasive mechanical ventilation or oxygen alone at randomization but not among those receiving no respiratory support.

In CoDex trial, 151 patients received 20mg of dexamethasone daily for 5 days, 10mg of dexamethasone daily for 5 days or until ICU discharge and standard care, 148 patients received standard care only.(5) Patients in the dexamethasone group had a mean 6.6 ventilator-free days (95% CI, 5.0-8.2) during the first 28 days vs 4.0 ventilator-free days (95% CI, 2.9-5.4) in the standard care group (difference, 2.26; 95% CI, 0.2-4.38;  $P = 0.04$ ). Thirty-three patients (21.9%) in the dexamethasone group vs 43 (29.1%) in the standard care group experienced secondary infections, 47 (31.1%) vs 42 (28.3%) needed insulin for glucose control, and 5 (3.3%) vs 9 (6.1%) experienced other serious adverse events. It was concluded that among patients with COVID-19 and moderate or severe ARDS, use of intravenous dexamethasone plus standard care compared with standard care alone resulted in a statistically significant increase in the number of ventilator-free days (days alive and free of mechanical ventilation) over 28 days.

[figure not shown]

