### **D. Research Design and Methods (What, When, How, Where)**

1. Identify sources of research material in the form of biospecimens, records and/or data from interaction with participants.  
The electronic medical records demographic and clinical data on participants

will be collected and analyzed.

2. Describe study design, including sequence and timing of study procedures. Distinguish research procedures from those that are routine care. Provide a flow diagram or timetable.

- It is a single center open label randomized clinical trial to investigate the different dose of dexamethasone on the health outcomes in hospitalized moderate or severe COVID patients.
- It is a superiority trial.
- This trial has two parallel groups. The participants will be randomly assigned in a 1:1 ratio to intervention group and control group.
- We anticipate that approximately 300 participants will be enrolled and complete the study (Each group will enroll 150 participants.) The study plan to start as soon as the OUHSC IRB approves it and the duration is 28 days.
- The COVID patients will be screened in the first 24 hours after investigators are contacted.
- Participants will be randomized to intervention arm or control arm after participants agree to be enrolled into the study and sign the informed consent.
- Except for the different doses of dexamethasone, participants will receive the routine medical care in OUMC.

3. Include the study duration and number of study visits required.

This study will last for 5 months. There is only one visit for patients who are in OUMC for more than 28 days after randomization. There are two visits for patients who are not in OUMC at day 28 after randomization, first visit is the same as prior mentioned first visit, the second visit is a phone visit. The first visit is for screening, informed consent. After the visit, participants will be randomized and receive dexamethasone 20mg daily vs. 6mg daily. Participants will receive other routine medical care in the hospital till discharge. Research staff will review the hospital medical records daily to monitor the clinical improvement and any adverse event. At day 28, if participants are not in OUMC, research team will contact participants to evaluate the WHO ordinal scale.

4. Describe blinding, including justification for blinding or not blinding the trial.

This is an open label trial. The study outcome is objective. Not blinding the trial does not affect the study outcome.

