5. Include justification for inclusion of a placebo or non-treatment group.

This study does not include a placebo or non-treatment group. At least two

large clinical trials showed corticosteroids have benefit to COVID patients. Using placebo or non-treatment is not ethic.

6. Describe what happens to participants receiving therapy when study ends or if their participation in the study ends prematurely.  
 Participation of the study ends after day 28. The investigator will not contact the participants or give other interventions or suggestions after day 28.  
 Participants are welcome to contact the PI for any questions after study participation ends.

7. Indicate where the procedures will be completed.

- Include all sites where research activities will be conducted (consenting, interventions, chart reviews, data analysis, etc).  
 This research will be conducted in University of Oklahoma Health Sciences Center. Consenting and interventions will be conducted in University of Oklahoma Medical Center. Chart reviews and data analysis will be conducted in University of Oklahoma Medical Center and College of Medicine.
- Indicate that all required approvals are already obtained or will be obtained at each research location prior to project implementation.  
 This trial will be conducted at OUMC adult service. OUHSC IRB approval is needed. No other approval is needed. We will collaborate with other clinical services including emergency department and hospitalist service for participant recruitment. [name], study Co-PI and chief of pulmonary and critical care section will facilitate the collaborations.

8. Indicate whether clinically relevant research results, including individual research results, will be disclosed to participants. If so, under what conditions? The individual research results, including the oxygen support information, the length of hospital stay, ICU care, ventilator use etc, will communicate with participants/guardians during routine patient care. The final deidentified data analysis results may be published in literatures.

9. Identifiers might be removed and the de-identified information may be used for future research without additional informed consent from the subject.

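### Once the 10-day course is complete, a harm that is neither fatal nor life-threatening cannot become a serious adverse event, so it misses expedited and IRB reporting until day 28

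*Combined protocol and SAP*

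**What the plan says.** Section N (Data and Safety Monitoring Plan) describes SAEs "as defined by deaths, life threatening conditions, or events requiring permanent discontinuation of the treatment". No other section widens the list. Prolonged hospitalization, readmission, lasting disability and other medically important events do not appear as criteria.

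SAE status carries specific duties in Section N: a case report form, notification of the principal investigator within 24 hours, follow-up until the event is over, submission to the IRB, and review singled out as a particular duty of the board.

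The treatment schedule is in the Abstract: "The intervention arm is dexamethasone 20mg daily for 5 days, followed by dexamethasone 10mg daily for 5 days", and "The comparator is dexamethasone 6mg daily for 10 days". Section D, item 6, sets the end of follow-up: "Participation of the study ends after day 28".

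On masking, Section D, item 4, says "This is an open label trial" and defends this with "Not blinding the trial does not affect the study outcome". On the expected steroid effects, Section K says "The providers will monitor the adverse effects closely and start appropriate treatment such as antibiotics and insulin".

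The plan also watches events that are not SAEs. Research staff check hospital records every day for adverse events (Section D, item 3). Infections, hyperglycaemia, lengths of stay, discharge disposition and 28-day status are collected (Section E). The board looks monthly at dexamethasone adverse events, including severe infection (Section N).

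**The concern.** Two of the three criteria describe how grave the event is. The third describes what the event requires to be done about treatment, and it is the only route for harms that are grave but do not threaten life. This raises two problems.

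- **Timing.** A criterion tied to discontinuing treatment can work only while there is treatment to discontinue. The course ends well before follow-up does.
- **Dependence on a judgement made with the dose known.** During the course, an infection or high glucose could be managed by adding treatment, as Section K describes, or could be judged to require stopping dexamethasone. Only the second makes it an SAE. Nothing in the plan provides for masked or independent classification of seriousness, and the board consists of the project investigators.

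What is at stake is mainly participant protection. Section K itself says that the higher-dose group may face more infection and hyperglycaemia. A severe but not life-threatening case arising after the course would bypass the fast reporting line and the IRB, which is the only reviewer of SAEs named in the plan that is not made up of the investigators.

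**Working it through.** There is no planned figure to reproduce; the point rests on the wording of a definition and on the treatment calendar.

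**Step 1: routes to SAE status (Section N).** Death; a threat to life; an event requiring permanent discontinuation. Remove the first two and one route is left.

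**Step 2: when that route is open.**
- High-dose course (Abstract): 5 + 5 = 10 days.
- Low-dose course (Abstract): 10 days.
- Follow-up (Section D, item 6): 28 days.
- Days after a completed course: 28 − 10 = 18.
- Share of follow-up: 18 / 28 = 0.643, or about 64%.

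This assumes that dosing starts at randomization and that the course is completed without gaps. A start one day later gives 17 / 28 = 61%. A course that ends early closes the route sooner. The result is a share of calendar days, not of events.

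**Step 3: one event followed through the plan.** Take a secondary infection on day 14 in a participant who completed the course. It prolongs the stay but is not life-threatening.

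| Item | Applies? | Source |
|---|---|---|
| Found by daily record review in the study hospital | Yes | Section D, item 3 |
| Recorded as an infection | Yes | Section E |
| Seen at the monthly board meeting, if severe | Yes, but possibly after the participant's day 28 | Section N |
| Qualifies as an SAE | No | Section N |
| 24-hour report, follow-up until it ends, IRB submission as an SAE | No | Section N |

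If the same infection led to readmission at another hospital, detection is also uncertain. Data come from the study hospital's database (Section E), and the day-28 call is described only as a way to score the ordinal scale (Section D, item 3).

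**Step 4: during the course.** The same infection on day 4 is an SAE if it is judged to require permanent discontinuation, and otherwise not. The dose is known when that judgement is made. The documents give no discontinuation rates for either arm, so no size or direction can be calculated.

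**The case against.** The strongest reply is that little is lost. Daily record review, planned data collection and monthly board review capture infections and hyperglycaemia whatever their SAE status and whatever the study day. The board may call for more frequent meetings and extra safety reports. Because all project investigators sit on the board and their staff read the charts daily, the principal investigator would probably hear of a severe inpatient infection anyway. This stands, and it limits the point: what is missing is the SAE designation and the duties attached to it, chiefly IRB submission, prompt notification and follow-up until the event ends. Monthly review by the investigators does not replace these.

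A reader might infer more, in two ways that the documents do not support.

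- **That SAE counts by arm will be biased.** Section N speaks of events that *require* discontinuation and names no one as deciding this. That the judgement would be made with the dose known follows from the open-label design, but that it would differ by dose is only a possibility. Section M plans descriptive statistics on adverse events and no between-arm test of SAEs. The loss of the discontinuation route after day 10 affects both arms alike, so it creates no imbalance by itself.
- **That the earlier high-dose trial in Section C shows how many events would be missed.** There, "Thirty-three patients (21.9%) in the dexamethasone group vs 43 (29.1%) in the standard care group experienced secondary infections". Those are all secondary infections, without timing or seriousness, in patients with moderate or severe ARDS and with standard care alone as comparator. The rate was lower on dexamethasone. They do not measure this gap.

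It is also fair to say that prolonged stay and medical importance are themselves judged with the dose known. The remedy closes the gap after the course and takes the treatment decision out of the definition; it does not mask the classification.

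**Conclusion.** The point holds as a gap in safety reporting. For a participant who completes the 10-day course, about 18 of 28 follow-up days (64%) have no SAE route other than death or a threat to life. A severe infection, readmission or lasting disability in that period would not trigger 24-hour notification, follow-up until it ends or IRB submission. This follows from the Abstract, Section D and Section N, given dosing from about the day of randomization.

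The second element is weaker: during the course, SAE status *can* depend on a discontinuation judgement made with the dose known. Whether this would produce a difference between arms, and in which direction, cannot be determined from the documents.

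Neither element touches the primary analysis. The number of events affected is unknown, and existing surveillance reduces the consequences for inpatients. The change is worth making because it is specific and cheap.

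**What to change.** In Section N:

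- Keep death and life-threatening conditions.
- Add prolonged hospitalization or readmission, persistent or significant disability, and other medically important events.
- State that SAEs are counted from randomization to day 28, whether or not dexamethasone is still being given.
- Record permanent discontinuation and its reason as a separate item, reported by arm.

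In Section D, item 3, add questions on readmission and serious events to the existing day-28 call, so that events treated elsewhere are found.

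Dosing and decisions about stopping treatment are left as they are. The cost is a short protocol amendment, a few questions on a call that is already planned, and modestly more SAE forms and IRB reports. As every participant is an inpatient at entry, the text should say briefly how prolongation of the stay will be judged.
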